### **Primary outcome:**

- Change in strength for each individual in each treatment group before and 30 minutes after CESI
- Categorical analysis based on a minimally clinically important change of 19.5% for upper extremity strength assessment (29).

### **Secondary outcomes:**

- Change in mean arterial pressure prior to, 30 minutes after CESI, via automated blood pressure cuff measure.
- Change in HR prior to, 30 minutes after CESI
- Change in NRS pain score from pre-injection to post injection (immediate) and 1-day.
- Change in UEFI score from pre-injection to post injection (immediate) and 1-day.
- Change in pain medication use from pre-injection to post injection (immediate) and 1-day.
- Procedure complications or adverse reactions to medications used

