**Introduction**

Cervical radicular pain is a common problem that is often treated by epidural steroid injection (1). While clinical practice guidelines do not specifically recommend or discourage the use of local anesthetic in the epidural injectate (2), the majority of the published literature on clinical outcomes of cervical epidural steroid injection includes the use of lidocaine in the epidural injectate (3-11). Consequently, many practitioners elect to use local anesthetic in the epidural injectate in order to obtain additional diagnostic information when the precise source of pain is not clear from clinical presentation and imaging. Local anesthetic may also be included in order to provide immediate pain relief in cases of painful acute radicular symptoms.

Local anesthetic injection into the epidural space has the potential to cause transient weakness of the upper extremities. High dose local anesthetic in the cervical epidural space (12) and inappropriately placed low-dose local anesthetic in the subdural space or subarachnoid space (13, 14) are known to cause motor weakness. Appropriately placed, low-dose local anesthetic injected into the epidural space via a transforaminal approach, in close proximity to the exiting spinal nerve root, causes motor block in a small proportion of patients (15). However, the effect of low-dose injection of local anesthetic in the cervical interlaminar epidural space on objective upper extremity strength has not been characterized in the published literature. This proposition affects post-procedure instructions, as even mild weakness may pose a hazard during performance manual activities that require the upper extremity/extremities such as using a handrail or cane handle for support.

Dynamometry is an established and validated method for assessing muscle strength and motor neuron function with high reliability, and has been used to objectively assess changes in upper extremity strength.

This study aims to determine whether a standard dose of 2 mL 1% lidocaine included as a steroid diluent in a C7-T1 cervical interlaminar epidural steroid injection (CESI) causes an objective change in strength as measured by dynamometry. We hypothesized that cervical epidural lidocaine will cause an objective decrease in strength in functional movements of the upper extremity.

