For Group 1 and Group 2, patients will be randomized to treatment group based on a random computer-generated schedule. Participants will be blinded to the group to which they are randomized. All standard procedures for CESIs will be followed as is standard practice including time out, skin prep, hemodynamic monitoring, image guidance, etc.

Per randomization, triamcinolone acetonide 80 mg (Kenalog) (E. R. Squibb & Sons Limited, Uxbridge UK) will be combined with 2mL Lidocaine 1% or 2 mL preservative free saline and will be injected during the CESI procedure. In all cases, the total injectate volume will be 4 mL. All injections will be image guided with fluoroscopy, as is the current standard practice. Fluoroscopy time will be recorded.

The participant will be discharged from the clinic with written discharge instructions (current standard practice).

Participants will be telephoned and emailed by clinic personnel 1 day after the CESI to assess for subjective weakness in the hands or arms as well as any other adverse reactions. As above, the UEFI will be administered at this time.

Participants will only be recruited for this study for a single CESI. Those who require repeat injections will not be recruited a second or third time.

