### **Study Termination Criteria**

- Adverse events considered/identified by the medical staff during the procedure process
- The subject requests to be withdrawn from the study during the procedure.

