### **Safety Monitoring Plan**

Safety will be monitored by all members of the study team:

[name]

[name]

The Principal Investigator is an MD at the University of Utah Orthopaedic Center and University of Utah South Jordan Health Center. Members of the data and safety monitoring committee will be in close contact with all the subjects throughout the study, both in-person and via telephone. The members of the data and safety monitoring committee will review potential side effects and adverse reactions with each subject at the time of delivery of the study drug and at the time of each sample collection. All the committee members are located at the University of Utah Orthopaedic Center; all members have research experience.

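### The adverse-event outcome is worded by cause, so falls or injuries that follow arm weakness need not be asked about or counted

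*Combined protocol and SAP*

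**What the plan says.** The last item under Secondary outcomes is the only outcome for adverse events: "Procedure complications or adverse reactions to medications used". Under Procedure, clinic personnel contact every participant 1 day after the injection "to assess for subjective weakness in the hands or arms as well as any other adverse reactions".

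Two other places touch on safety. Study Termination Criteria lists "Adverse events considered/identified by the medical staff during the procedure process", which is not limited by cause but is a stopping criterion confined to the procedure. Under the Safety Monitoring Plan, committee members "will review potential side effects and adverse reactions with each subject at the time of delivery of the study drug". The other occasion named there is sample collection, and no sampling is described under Procedure.

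The supplied text does not define an adverse event, require recording whatever the cause, state who assigns cause and by what rule, or mention falls or injuries. Statistical analysis gives Fisher's exact test for strength and descriptive statistics for demographics, pain and UEFI. It gives nothing for adverse events.

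The Introduction ties the trial to post-procedure instructions because "even mild weakness may pose a hazard during performance manual activities that require the upper extremity/extremities such as using a handrail or cane handle".

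**The concern.** To call an event a complication of the procedure or a reaction to a drug is already to assign it a cause. Someone who slips on the stairs that evening because a hand would not grip the rail has had a fall. Neither the participant nor the caller need think of it as a drug reaction, and nothing in the text obliges anyone to record it. Yet this is the kind of event that the post-procedure instructions are meant to prevent.

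In a randomized trial the comparison between arms carries the information on cause, so events can be recorded without attribution and classified afterwards. A filter at collection loses events that cannot be recovered later. What is at stake is whether the trial can say how many participants in each arm came to harm after discharge, alongside what it will say about strength.

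**Working it through.** **1. What is recorded, and whether it depends on cause**

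| Section | Item | Timing | Limited by cause? |
|---|---|---|---|
| Primary outcome; Procedure | Dynamometry, with a 19.5% threshold | 30 minutes | No |
| Procedure | Subjective weakness question | Day 1 | No |
| Procedure; Secondary outcomes | UEFI | Day 1 | No |
| Secondary outcomes | Blood pressure, heart rate | 30 minutes | No |
| Secondary outcomes | Complications, drug reactions | Not stated | Yes |
| Procedure | Other adverse reactions | Day 1 | Yes |
| Study Termination Criteria | Adverse events | During the procedure | No, but it ends before discharge |

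A fall at home that evening is outside every row not limited by cause: those rows measure impairment, function or vital signs, or stop at the procedure. It enters a cause-limited row only if someone links it to the injection or a drug. The gap is therefore the consequences of weakness, not weakness itself.

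**2. The plan's own figures**

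Inputs from Power Analysis: 52 per arm, 20% with a deficit on lidocaine, 2% measurement error (taken as the saline rate), nominal alpha 0.05, Fisher's exact test. Sidedness is not stated.

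Power = Σ Bin(x; 52, 0.20) · Bin(y; 52, 0.02), summed over all tables (x, y) with two-sided Fisher p ≤ 0.05. Result: 0.803, which agrees with the stated power above 80%. The same sum with 2% in both arms gives 0.0004, the stated achieved level. The plan's figures reproduce, and adverse-event recording does not enter them.

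**3. How many injuries might be at issue**

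The documents give no injury rate, so this is for scale only. Assumptions: 20% of the lidocaine arm are weak (the Power Analysis figure), the weakness lasts long enough to matter after discharge, and a fraction q of those weak are injured.

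- Expected number = 52 × 0.20 × q
- Chance of at least one = 1 − (1 − 0.20q)^52

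| q | Expected in 52 | Chance of at least one |
|---|---|---|
| 5% | 0.52 | 41% |
| 10% | 1.04 | 65% |
| 20% | 2.08 | 88% |

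**4. Whether such counts could be tested**

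For x events against 0 with 52 per arm, two-sided Fisher p = 2 × C(52, x) / C(104, x).

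- x = 5: 2 × 2,598,960 / 91,962,520 = 0.057
- x = 6: 2 × 20,358,520 / 1,517,381,580 = 0.027

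At least 6 v 0 is needed. At the top of the range above (0.20 × 0.20 = 4%, against 0%), power is P(X ≥ 6) with X ~ Bin(52, 0.04), about 1.7%. Injury counts can be described but not tested.

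**The case against.** The strongest reply is that arm weakness is the harm under study and is already captured in three ways that need no attribution. That stands, and it narrows the point to what weakness leads to.

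Second, the day-1 question is put to everyone and is open-ended, and no section says that a fall caused by weakness is not a procedure complication. A good caller might well elicit one. That also stands, but it leaves recording to the caller's reading of the words.

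Third, Procedure refers to a Report Form in an appendix that is not in the supplied text. It may hold a fall or general adverse-event item, so absence from the trial cannot be shown, only absence from the text available.

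A reader might go further and infer that the arms will be compared on opinion. The documents do not support this: no judging step, assessor or criteria are described, and no between-arm analysis of adverse events is stated. A reader might also infer that attribution would create a false difference, because visibly weak participants are more likely to have events ascribed to the drug. Study design labels the trial double blinded, although Procedure describes blinding of participants only. Unequal attribution is conceivable, but nothing in the documents shows it, and any figure for it would rest on invented rates.

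**Conclusion.** The point holds as a gap in collection and definition. Under the text as written, falls and injuries after discharge need not be asked about or counted unless someone links them to the procedure or a drug, although the Introduction rests the trial's practical value on that kind of hazard. The conclusion assumes that the Report Form adds no such item.

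The size is modest. On the assumed rates, 0.5 to 2.1 injuries would be expected in the lidocaine arm, too few to test. The primary analysis, the sample size of 52 per arm and the power of 0.803 are unaffected. With so few events each one matters to the description, and the change is cheap enough to be worth making.

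**What to change.** Under Secondary outcomes, replace the adverse-event item with: *All adverse events from injection to the day-1 contact, whatever the judged cause, reported by arm as number and percentage of participants with a difference and 95% confidence interval, descriptively; procedure complications and suspected drug reactions shown as subsets.*

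Under Procedure, have the existing day-1 contact ask about *any adverse event, including falls or injuries since discharge*, alongside the weakness question. Align the Report Form, or confirm that it already has the item.

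Settle the time window. Procedure and Secondary outcomes end at day 1, whereas Data Analysis Plan describes a 1-month assessment. If that assessment belongs to this trial, the sections must be reconciled and later events reported as a separate window, so that unrelated events over a month do not obscure those near the injection.

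Cost: wording in two sections, about one more question at a contact already scheduled, and some noise from unrelated events, which the subsets help to separate. No design figure changes.

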### **Risks/Benefits:**

Risks of study participation are the same as those for any standard fluoroscopically guided cervical ESI performed for management of cervical radiculitis when more conservative methods have been exhausted or failed. These risks include: local infection, epidural hematoma or abscess, dural puncture and potential post-dural puncture headache, paresthesia during needle placement, pain at the injection site, failure of technique to decrease pain levels, allergy to latex,

iodine/chlorhexidine, adhesives or any medications used during the procedure. Utilizing fluoroscopy, the risk of nerve damage, spinal cord injury or intravascular injection is less than 1:500,000. The length of stay and length of recovery is no longer than that of a standard ESI performed in the PM&R Spine Clinic at present.

There are no risks associated with the pre- and post-injection grip and arm strength testing with dynamometry. In this study, the length of stay and length of recovery is no longer than that of a standard CESI performed in the Orthopaedic Center at present.

There are no direct benefits to the individual by participating in this study. The patients will be presented with the same treatment options whether they enroll in the study or decide not to participate. The information gained from this study may provide the investigators a better understanding of a patient's pain and strength response following a cervical epidural steroid injection.

### **Study Termination Criteria**

- Adverse events considered/identified by the medical staff during the procedure process
- The subject requests to be withdrawn from the study during the procedure.

### **Safety Monitoring Plan**

Safety will be monitored by all members of the study team:

[name]

[name]

The Principal Investigator is an MD at the University of Utah Orthopaedic Center and University of Utah South Jordan Health Center. Members of the data and safety monitoring committee will be in close contact with all the subjects throughout the study, both in-person and via telephone. The members of the data and safety monitoring committee will review potential side effects and adverse reactions with each subject at the time of delivery of the study drug and at the time of each sample collection. All the committee members are located at the University of Utah Orthopaedic Center; all members have research experience.

